9.7.1.6 Efficacy Analyses

The FAS will be used as the primary analysis set for all efficacy analyses, while the PP will be used as a supportive analysis. Unless specified otherwise, a 2-sided $\alpha=0.05$ significance level will be used for all efficacy analyses.

Primary Efficacy Analysis

The primary efficacy endpoint is the change in BMI from Baseline to Week 52. The change from baseline in BMI will be analyzed using the repeated measures analysis of covariance model (ANCOVA) with factors of treatment, visits (Baseline, Week 1, 5, 8, 12, 20, 28, 36, 44, and 52), sex (male and female), treatment-by-visit interaction as fixed effect, subjects as random effect, and the baseline age and BMI as covariates. The missing values will be imputed using a pattern mixture model utilizing multiple imputation (MI) using the same model as the analysis model. The missing values will be imputed for a visit at a time using the complete cases up to and include the current visit for a particular visit. The unstructured covariance matrix will be used in the analysis and the treatment comparison at Week 52 will be the event of interest. In case of a convergence issue, the Toeplitz covariance structure will be used in the model. As a sensitivity analysis, the missing values will also be imputed using pattern mixture MI method assuming the missing value is missing not at random (MNAR). The details of the analysis model and missing value imputation method will be further described in the SAP.

In addition, the following analyses will also be considered as sensitivity analyses:

- PP analysis: The same primary efficacy analyses described above will be repeated based on the PP.
- Change from baseline in standardized BMI score (Z-score): The same primary efficacy analyses described above will be repeated using Z-score.

Subgroup analyses and additional sensitivity analyses, if appropriate, may also be performed and will be described in the SAP.

Key Secondary Efficacy Analysis

The key secondary efficacy endpoint is the proportion of subjects achieving at least a 5% BMI reduction at Week 52. The secondary efficacy endpoint will be analyzed only if the test for the primary efficacy endpoint is statistically significant.

The proportion of subjects achieving at least a 5% BMI reduction at Week 52 will be analyzed using a logistic regression model with factors of treatment, and sex (male and female), and baseline BMI as a covariate using FAS. Subjects with any missing assessment at Week 52 will be considered as treatment failures in this analysis.

Other Secondary Efficacy Analyses

Unless specified, for all other secondary efficacy endpoints, the continuous variables will be analyzed using mixed effect model repeated measurement analysis (MMRM) and categorical variables will be analyzed using the Cochran Mantel Haenszel test, Chi-square test, or logistic regression as appropriate. Additional analysis may be performed as needed using appropriate statistical methodologies as specified in SAP.

Subgroup analyses will be performed on the primary efficacy endpoint, including sex (male and female), race (white, black, Asian, and other). Additional subgroups may be explored, if deemed necessary.

No adjustment for multiplicity is planned for other secondary endpoints, subgroup, and sensitivity analyses.

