9.7.2 Determination of Sample Size

The proposed sample size is based on the comparison of the primary efficacy endpoint, change from Baseline in BMI at Week 52 between the Belviq XR 20-mg treatment group and placebo group. Assuming a SD of 2.2 kg/m² and a 40% dropout rate, a sample size of 360 subjects in a 1:1 ratio (n=180 in the Belviq XR 20-mg treatment group; n=180 in the placebo group) will have at least 90% power to detect a treatment difference of 1 kg/m² in BMI, using a 2-sided t-test with $\alpha=0.05$. Assuming the proportion of subjects achieving at least a 5% BMI reduction at Week 52 is 20% for the placebo group and a 40% dropout rate, this sample of 360 subjects (180 subjects for Belviq XR 20 mg and 180 subjects for placebo) will also have greater than 85% power to detect an absolute difference of 20% between the Belviq XR 20-mg group and placebo group, using a 2-sided Fisher's Exact test with $\alpha=0.05$. The assumption used in the sample size calculation is based on the 2 pivotal lorcaserin studies, APD356-009 and APD356-011 in obese and overweight non-diabetic adult subjects.

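### Baseline is a visit level of a change-from-baseline outcome, so the primary model as written is degenerate and is sent to a Toeplitz fallback that can understate the Week 52 standard error

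*Protocol*

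**What the plan says.** The text is the Primary Efficacy Analysis in Protocol section 9.7.1.6, in the newest version in the file (ages 12 to 17, stratified by sex).

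- Outcome: "The change from baseline in BMI will be analyzed using the repeated measures analysis of covariance model (ANCOVA").
- Visit factor and interaction: "visits (Baseline, Week 1, 5, 8, 12, 20, 28, 36, 44, and 52), sex (male and female), treatment-by-visit interaction as fixed effect".
- Remaining terms: "subjects as random effect, and the baseline age and BMI as covariates". No covariate-by-visit terms are listed, so each covariate has one slope for all visits.
- Covariance and target: "The unstructured covariance matrix will be used in the analysis and the treatment comparison at Week 52 will be the event of interest".
- Fallback: "In case of a convergence issue, the Toeplitz covariance structure will be used in the model".
- Deferral: "The details of the analysis model and missing value imputation method will be further described in the SAP".

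Missing values are multiply imputed visit by visit, with the analysis model also serving as the imputation model. The per-protocol and Z-score sensitivity analyses repeat the same model. The key secondary endpoint is tested only if the primary test is significant.

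**The concern.** Change from baseline at Baseline is a column of zeros. Giving it a visit level in an unstructured 10 × 10 covariance asks the model to estimate a variance that is exactly zero. The primary model then cannot be fitted as stated, and the rule for convergence trouble takes over.

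Plain Toeplitz normally means one variance for all visits and a correlation that depends only on the number of visits apart. If the spread of BMI change grows over the year, a pooled variance is smaller than the Week 52 variance. The all-zero Baseline row pulls it down further. The Week 52 confidence interval would then be too narrow and the primary p-value too small. That p-value also opens the key secondary test, and the same specification carries into the imputation and the two sensitivity analyses.

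**Working it through.** **1. The plan's own figures.** Inputs from section 9.7.2: "Assuming a SD of 2.2 kg/m² and a 40% dropout rate", 360 subjects at 1:1, difference 1 kg/m², two-sided 0.05.

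- Evaluable per arm: 180 × 0.6 = 108.
- SE of the Week 52 difference: 2.2 × √(2/108) = 0.299.
- Power: Φ(1/0.299 − 1.96) = 91.6% (normal), or 91.4% (noncentral t). The stated figure of at least 90% is reproduced.
- Fisher's exact test, 20% against 40%, 108 per arm: 87.1%. The stated figure above 85% is reproduced.

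**2. The unstructured model with Baseline as a level.** The true covariance of the ten changes has rank 9. If the Baseline mean is set to 0 and the common covariate slopes go to 0, the Baseline residual variance goes to 0 and its log-likelihood term, −(N/2)·log(variance), goes to +∞. On simulated data (N = 360, ten visits, one covariate with true slope 0.30) the profile log-likelihood was:

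| Slope held at | 0.3 | 0.1 | 0.01 | 10⁻⁴ | 10⁻⁸ |
|---|---|---|---|---|---|
| Log-likelihood | −51 | 345 | 1174 | 2831 | 6147 |

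From 10⁻⁴ to 10⁻⁸ the Baseline variance falls by a factor of 10⁸. The predicted gain is 180 × ln(10⁸) = 3316, and 6147 − 2831 = 3316. There is no maximum. Without the Baseline level, the same data give a proper maximum of −341 at slope 0.29.

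**3. The subject random effect.** The marginal covariance is V = R + g·J, with J a matrix of ones. Taking R = V − g·J with g = 0, 0.02 and 0.05 gave a positive-definite R and the same V each time. The term cannot be identified beside an unstructured R, but V and the Week 52 SE are unchanged.

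**4. The Toeplitz fallback.** The document gives no SD for any visit before Week 52, so nine patterns were assumed, all scaled to SD 2.2 at Week 52. For each true covariance S, the equal-variance Toeplitz matrix T minimising log|T| + tr(T⁻¹S) was found. The SE ratio is √(T variance)/2.2, which does not depend on sample size. The rejection rate under no effect is 2·(1 − Φ(1.96 × ratio)).

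| Assumed pattern | SD at Week 1 | Ratio (error), Baseline kept | Ratio (error), Baseline removed |
|---|---|---|---|
| Random walk | 0.31 | 0.658 (19.7%) | 0.684 (18.0%) |
| Random slope, error SD 0.3 | 0.43 | 0.711 (16.3%) | 0.742 (14.6%) |
| Random slope, error SD 0.5 | 0.71 | 0.672 (18.8%) | 0.715 (16.1%) |
| Stationary BMI, weekly correlation 0.99 | 0.34 | 0.671 (18.9%) | 0.699 (17.1%) |
| Stationary BMI, weekly correlation 0.95 | 0.51 | 0.736 (14.9%) | 0.771 (13.1%) |
| SD linear from 0.4 | 0.40 | 0.645 (20.6%) | 0.669 (19.0%) |
| SD linear from 1.1 | 1.10 | 0.700 (17.0%) | 0.764 (13.4%) |
| SD linear from 1.8 | 1.80 | 0.810 (11.2%) | 0.906 (7.6%) |
| Flat 2.2 after Baseline | 2.20 | 0.897 (7.9%) | 1.000 (5.0%) |

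The last four patterns use a correlation of 0.9 per visit step. At 108 per arm, the SE with Baseline kept is 0.193 to 0.269 against a true 0.299.

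**5. Allowing for multiple imputation.** The total variance adds a between-imputation part. If a fraction f of the information is missing and Toeplitz shrinks only the within-imputation part, the overall ratio is √((1 − f)·ratio² + f). The document gives no f; 0.3 is assumed, with 0.2 and 0.4 as a range.

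- f = 0.3, ratio 0.645: √(0.7 × 0.416 + 0.3) = 0.769, error 13%.
- f = 0.3, ratio 0.897: √(0.7 × 0.805 + 0.3) = 0.929, error 7%.
- f = 0.2: overall ratios 0.730 and 0.919, errors 15% and 7%.
- f = 0.4: overall ratios 0.806 and 0.940, errors 11% and 7%.

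**The case against.** The strongest reply is that the harm needs a chain of choices. The programmer must enter the zero Baseline rows, respond to the failure by switching to Toeplitz instead of dropping those rows, use the equal-variance form, and use no robust variance. A sensible analyst would probably break the chain, and the section defers model details to the SAP, which is not shown. Covariate-by-visit terms are ordinary SAP content, and their absence is not held against the protocol.

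This limits the size of the point but does not remove it. The visit levels, the covariance and the fallback are stated in the protocol, not left open. A SAP that follows them inherits the fault, and one that departs from them contradicts the protocol on its primary analysis. The possible repairs also give different Week 52 standard errors.

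Three stronger readings are tempting and are not supported:

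- *The subject random effect makes the model unfittable.* It is redundant, but step 3 shows that it leaves the Week 52 inference alone. The Baseline level is the cause.
- *Type I error is 15% to 21%.* Such figures arise when variance grows markedly over time and between-imputation variance is ignored. The document supports neither as a fact.
- *Toeplitz understates the SE in every case.* With Baseline removed and flat post-baseline variance, it does not.

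In the other direction, if the imputations were themselves drawn from a Toeplitz model, the relief in step 5 would shrink; the section does not settle this. Finally, only the last of three parts of the file is at hand, so this may not be the final protocol text.

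**Conclusion.** The specification is wrong as written. Taken literally, the primary model has no maximum-likelihood fit because of the Baseline level, and the plan's own rule then sends the primary analysis to Toeplitz.

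The consequence is conditional on assumed visit-wise variances, an equal-variance Toeplitz and no robust SE. With the Baseline row kept, the complete-data Week 52 SE is about 10% to 35% too small in the patterns tried. The nominal 5% test then runs at about 8% to 21% without between-imputation variance, or roughly 7% to 13% with 30% missing information and an unaffected imputation variance.

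With Baseline removed, the unstructured model can be fitted and the fallback is no longer forced. If Toeplitz were still used, the error rate would run from 5% (no inflation) to about 19%, again ignoring between-imputation variance. A reader might also infer that the sample size is wrong; it is not, because every stated power figure reproduces and none depends on this model.

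**What to change.** In section 9.7.1.6:

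1. Remove Baseline from the visit factor, leaving the nine post-baseline visits (Weeks 1, 5, 8, 12, 20, 28, 36, 44 and 52).
2. Delete the subject random effect; the unstructured matrix already carries the within-subject correlation.
3. Restate the fallback as a heterogeneous-variance structure, for example heterogeneous Toeplitz, with a robust (sandwich) standard error.

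Carry the same wording into the imputation model, the per-protocol and Z-score analyses, and the SAP. The cost is a change of protocol and SAP text. Data collection, sample size and power statements stay as they are.

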9.7.1.7 Pharmacokinetic, Pharmacodynamic, Pharmacogenomic, and Other Biomarker Analyses

9.7.1.7.1 PHARMACOKINETIC ANALYSES

Lorcaserin plasma concentration-time data will be subjected to population PK analysis using nonlinear mixed effects modeling. The effect of covariates, such as baseline characteristics or demographics, on PK will be explored. Derived exposure parameters such as the maximum observed concentration and the area under the concentration-time curve from time 0 to 24 hours at steady-state will be calculated from the final PK model using individual posterior estimates of the PK parameters and from dosing history. The PK analysis set will be used for this analysis.

9.7.1.7.2 PHARMACODYNAMIC ANALYSES

Change from Baseline in BMI will be assessed as the PD analysis. The PD analysis set will be used for this analysis.

Other assessments (eg, percentage of BMI change, proportion [%] of patients achieving $\geq 5\%$ and $\geq 10\%$ BMI reduction, and change in waist circumference from baseline) will also be assessed as part of the PD analysis. The PK/PD analysis set will be used for this analysis.

9.7.1.7.3 PHARMACOKINETIC/PHARMACODYNAMIC ANALYSES

Population PK/PD modeling will be used to explore the relationship between lorcaserin plasma exposure and response, including but not limited to change in BMI from baseline and the probability of achieving at least a 5% and at least a 10% change in BMI from baseline to Week 52. Additionally, exposure-safety relationships for select safety parameters may be explored graphically, depending on the data at the end of study. Any emergent relationship may be modeled as appropriate. Any parameters based on the study data may be considered for exploratory assessment for its relationship to PK.

9.7.1.7.4 PHARMACOGENOMIC AND PHARMACOGENETIC ANALYSES

Not applicable

9.7.1.8 Safety Analyses

Evaluations of safety will be performed on the Safety Analysis Set. Safety assessments including the incidence of AEs (including changes from baseline in physical examination), growth (CDC growth chart and bone age determined by x-ray of the hand), sexual maturation (Tanner Staging), out-of-normal-range laboratory safety test values, change from baseline in laboratory safety test values, ECGs, and vital sign measurements will be summarized by treatment group using descriptive statistics or frequency count as appropriate. In addition, cognitive function will be evaluated by the WRAML-2, depression will be evaluated by the PHQ-9, and suicidal ideation and behavior will be evaluated by the C-SSRS, and will also be summarized by treatment group using descriptive statistics or frequency count as appropriate. All WRAML-2 raw scores from the Core Battery will be converted to age and gender standard scores for purposes of intra individual comparisons. For echocardiographic assessments, the proportion of subjects who develop FDA-defined valvulopathy, the proportion of subjects who develop pulmonary hypertension [pulmonary hypertension is defined when the subject's systolic pulmonary artery pressure (SPAP) ≥ 40 mmHg evaluated by echocardiograph], and change from baseline in SPAP will be summarized by treatment group at Week 28 and Week 52 using descriptive statistics or frequency count as appropriate.

No hypothesis testing will be performed for the safety assessment.

Study Day 1 for all safety analyses will be defined as the date of the 1st dose of study drug.

9.7.1.8.1 EXTENT OF EXPOSURE

Subjects will receive Belviq XR 20 mg or placebo QD for up to 52 weeks. The extent of exposure will be characterized by duration of exposure (in weeks) for each treatment group.

Duration of exposure will be defined as the number of weeks between the date the subject received the 1st dose of study drug and the date the subject received the last dose of study drug. Duration of exposure will be summarized using descriptive statistics by treatment group. In addition, the duration of exposure will be categorized and will be summarized using frequency count by treatment group.

9.7.1.8.2 ADVERSE EVENTS

The AE verbatim descriptions (investigator terms from the CRF) will be classified into standardized medical terminology using the Medical Dictionary for Regulatory Activities (MedDRA). Adverse events will be coded to the MedDRA (Version 18.0 or higher) lower level term closest to the verbatim term. The linked MedDRA PT and primary system organ class (SOC) are also captured in the database.

A treatment-emergent AE (TEAE) is defined as an AE that emerges during treatment (up to 28 days after the last dose of study drug), having been absent at pretreatment (Baseline) or

- Reemerges during treatment (up to 28 days after the last dose of study drug), having been present at pretreatment (Baseline) but stopped before treatment, or
- Worsens in severity during treatment relative to the pretreatment state, when the AE is continuous.

Only those AEs that were treatment emergent will be included in summary tables. All AEs, treatment emergent or otherwise, will be presented in subject data listings.

The TEAEs will be summarized by treatment group. The following summaries will be reported for TEAES:

- Incidence of TEAEs in descending order of frequency
- Incidence of TEAEs by SOC and PT
- Incidence of treatment-related TEAEs by SOC and PT
- Incidence of TEAEs by SOC, PT and maximum severity (mild, moderate, or severe)
- Incidence of treatment-related TEAEs by SOC, PT, and maximum severity (mild, moderate, or severe)
- Incidence of TEAEs by SOC, PT, and relationship to study drug (Yes [related] or No [not related])

A subject will be counted only once within a SOC or PT, if the subject experienced more than 1 TEAE within a specified SOC and PT.

The following summaries will also be presented for the treatment-emergent SAEs.

- Incidence of TEAEs leading to death
- Incidence of treatment-emergent SAE by SOC and PT
- Incidence of treatment-related treatment-emergent SAE by SOC and PT

In addition, subjects with TEAEs leading to discontinuation from study drug and AEs of special interest as described in Section 9.5.4.3.2 will be summarized by MedDRA SOC and PT for each treatment group.

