9 INVESTIGATIONAL PLAN

9.1 Overall Study Design and Plan

This is a multicenter, randomized, double-blind, placebo-controlled, parallel-group study in obese adolescents ages 12 to 17 years. Approximately 360 subjects will be randomized in a 1:1 ratio to Belviq XR 20 mg QD (180 subjects) and placebo (180 subjects). Subjects will be stratified by sex. Subjects will receive Belviq XR 20 mg or placebo QD in a 1:1 ratio for up to 52 weeks. Throughout the duration of the study, subjects will be encouraged to adhere to a lifestyle modification program that includes a standardized, age-appropriate diet and exercise counseling (see [Appendix 2](#)).

The study will consist of 2 phases: Prerandomization and Randomization. The Prerandomization Phase will last up to 30 days and consists of 1 visit during which subjects will be screened for eligibility. The Randomization Phase consists of a Treatment Period and a Follow-Up Period. The Treatment Period will last for a maximum of 52 weeks, with visits at Weeks 1, 5, 8, 12, 20, 28, 36, 44, and 52; the Follow-Up Period will extend from the End of Treatment (EOT) visit to the End of Study (EOS) visit.

Subjects who screen fail can be re-screened only once after 60 days. All subjects will continue in the study until the 52-week evaluation is completed. Subjects who discontinue treatment prematurely will be followed up until study completion.

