9.5.1.5.1 ADVERSE EVENTS AND EVENTS ASSOCIATED WITH SPECIAL SITUATIONS

An AE is any untoward medical occurrence in a patient or clinical investigation subject administered an investigational product. An AE does not necessarily have a causal relationship with the medicinal product. For this study, the study drug is Belviiq XR (lorcaserin hydrochloride).

The criteria for identifying AEs in this study are:

- Any unfavorable and unintended sign (including an abnormal laboratory finding), symptom, or disease temporally associated with the use of an investigational product, whether or not considered related to the investigational product (Note: Every sign or symptom should not be listed as a separate AE if the applicable disease [diagnosis] is being reported as an AE)
- Any new disease or exacerbation of an existing disease
- Any deterioration in non-protocol-required measurements of a laboratory value or other clinical test (eg, ECG, x-ray) that results in symptoms, a change in treatment, or discontinuation of study drug
- Recurrence of an intermittent medical condition (eg, headache) not present pretreatment (Baseline)
- An abnormal laboratory test result should be considered an AE if the identified laboratory abnormality leads to any type of intervention, withdrawal of study drug, or withholding of study drug, whether prescribed in the protocol or not.

All AEs observed during the study will be reported on the Adverse Event CRF. All AEs, regardless of relationship to study drug or procedure, should be collected beginning from the time the subject signs the study ICF through the last visit in the Treatment Phase. Subjects who fail screening primarily due to AE(s) must have the AE(s) leading to screen failure reported on the Screening Disposition CRF. SAEs will be collected for 28 days after the last dose.

Abnormal laboratory values should not be listed as separate AEs if they are considered to be part of the clinical syndrome that is being reported as an AE. It is the responsibility of the investigator to review all laboratory findings in all subjects and determine if they constitute an AE. Medical and scientific judgment should be exercised in deciding whether an isolated

laboratory abnormality should be classified as an AE. Any laboratory abnormality considered to constitute an AE should be reported on the Adverse Event CRF.

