Abnormal ECG (corrected QT interval [QTc]) results, if not otherwise considered part of a clinical symptom that is being reported as an AE, should be considered an AE if the QTc interval is greater than 450 msec and there is an increase of more than 60 msec from baseline. Any ECG abnormality that the investigator considers as an AE should be reported as such.

It is the responsibility of the investigator to review the results of the C-SSRS, PHQ-9, and WRAML-2 in all subjects and determine if any result constitutes an AE. Medical and scientific judgment should be exercised in deciding whether an isolated suicidality rating scale response should be classified as an AE (see [Section 9.5.1.5.9](#) for a description of the C-SSRS).

All AEs must be followed for 28 days after the subject's last dose or until resolution, whichever comes first. All SAEs must be followed to resolution or, if resolution is unlikely, to stabilization.

Every effort must be made by the investigator to categorize each AE according to its severity and its relationship to the study treatment.

Assessing Severity of Adverse Events

Adverse events will be graded on a 3-point scale (mild, moderate, severe) and reported in the detail indicated on the CRF. The definitions are as follows:

Mild Discomfort noticed, but no disruption of normal daily activity

Moderate Discomfort sufficient to reduce or affect normal daily activity

Severe Incapacitating, with inability to work or to perform normal daily activity

The criteria for assessing severity are different than those used for seriousness (see [Section 9.5.1.5.2](#) for the definition of an SAE).

Assessing Relationship to Study Treatment

Items to be considered when assessing the relationship of an AE to the study treatment are:

- Temporal relationship of the onset of the event to the initiation of the study treatment
- The course of the event, especially the effect of discontinuation of study treatment or reintroduction of study treatment, as applicable
- Whether the event is known to be associated with the study treatment or with other similar treatments
- The presence of risk factors in the study subject known to increase the occurrence of the event

- The presence of nonstudy, treatment-related factors that are known to be associated with the occurrence of the event

Classification of Causality

The relationship of each AE to the study drug will be recorded on the CRF in response to the following question:

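### The worsening limb of the TEAE definition omits the 28-day post-dose window that the other two limbs carry, so a pre-existing continuous AE that first worsens after the last dose is listed but not tabulated

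*Protocol*

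**What the plan says.** Section 9.7.1.8.2 (Adverse Events) opens the definition with new events: "A treatment-emergent AE (TEAE) is defined as an AE that emerges during treatment (up to 28 days after the last dose of study drug", for events absent at Baseline. The second limb covers events that had been present but had stopped before treatment: "Reemerges during treatment (up to 28 days after the last dose of study drug", with the same window written out again. The third covers continuing events: "Worsens in severity during treatment relative to the pretreatment state, when the AE is continuous". No period after the last dose is given there.

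The same section fixes what follows from the classification: "Only those AEs that were treatment emergent will be included in summary tables". For everything else, "All AEs, treatment emergent or otherwise, will be presented in subject data listings".

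The data rules reach past the last dose. Section 9.5.1.5.1 says "All AEs must be followed for 28 days after" the last dose, or until resolution if that comes first, and "SAEs will be collected for 28 days after the last dose". Section 9.1 adds: "Subjects who discontinue treatment prematurely will be followed up until study completion".

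**The concern.** The three limbs together are meant to decide which AEs belong to the treatment period. Two of them treat the four weeks after the last dose as part of that period and the third, on its face, does not. Like events are then classified differently: on the same post-dose day, a new event and a returning event are treatment emergent, while the first worsening of a continuing one is not.

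Every AE summary in the section is built on treatment-emergent events, including the tables by maximum severity and those for treatment-emergent SAEs. An event that misses the definition misses all of them. The protocol gives no reason for handling worsening differently, and a SAP that copies the definition would inherit the gap.

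**Working it through.** No arithmetic applies, because the point rests on wording and the plan states no figure to reproduce. The check sets the three limbs side by side and runs cases through them.

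**The limbs as written (Section 9.7.1.8.2)**

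| Limb | Status before treatment | Window stated |
|---|---|---|
| 1. Emerges | Absent | During treatment, to 28 days after last dose |
| 2. Re-emerges | Present, but stopped before treatment | During treatment, to 28 days after last dose |
| 3. Worsens | Present and continuous | During treatment |

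**Cases, each with an event dated between 1 and 28 days after the last dose**

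1. Absent at Baseline, first appears in the window: limb 1 applies. Tabulated.
2. Present before, stopped before treatment, returns in the window: limb 2 applies. Tabulated.
3. Began on treatment, continues, worsens in the window: already treatment emergent under limb 1 from its onset. Tabulated.
4. Present before treatment, continuous, had already worsened on drug, worsens again in the window: already treatment emergent under limb 3. Tabulated.
5. Present before treatment, continuous, no worse on drug, first worsens in the window: limb 1 fails (not absent at Baseline), limb 2 fails (never stopped), limb 3 fails (no worsening during treatment). Listed only.

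Only case 5 falls through.

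**Can case 5 arise, and would it be recorded?** AEs are collected from consent (Section 9.5.1.5.1) and screening runs from Day -30 to Day -1 (Table 2), so an AE can begin before the first dose and continue. Ongoing AEs are followed for 28 days after the last dose, AE monitoring is scheduled at the Week 56 visit (Table 2), and early stoppers stay under observation. The worsening would be captured and then left out of the tables.

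**Does the protocol's history suggest intent?** The oldest protocol version reproduced in the file has no post-dose window in any limb. The later versions add it to limbs 1 and 2 only. That looks like a drafting slip rather than a choice.

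**The case against.** Four arguments deserve an answer.

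*The first limb may define the term.* The parenthesis in limb 1 could be read as explaining what *during treatment* means throughout, in which case limb 3 inherits it. This is possible but weak. Limb 2 repeats the parenthesis, which would be unnecessary if limb 1 had settled the meaning, and limb 3 then leaves it out.

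*Post-dose worsening may be entered as a new AE.* Conditions present at entry go on the medical history form, and Section 9.5.1.5.1 makes exacerbation of an existing disease an AE in its own right. A site could record the exacerbation with its own onset date, and limb 1 might then catch it. This narrows the gap for medical-history conditions but does not close it: limb 1 requires absence at Baseline, and sites or programmers could reasonably decide either way. AEs that begin between consent and first dose are not helped.

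*The consequence is limited.* This stands. The events remain in the listings, SAE collection and reporting do not depend on the classification, and Section 9.7.1.8 rules out hypothesis testing on safety.

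*The SAP may settle it.* Section 9.7.1 leaves further detail to the SAP, which is not shown. But the protocol already fixes the definition, so the wording should be right there.

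A reader might also infer that any continuing AE that worsens after the last dose is lost, or that post-treatment headache or mood complaints drop out. The documents do not support this. Cases 3 and 4 above are counted. An intermittent complaint that had stopped and then returns belongs to limb 2, which has the window. Depressive disorders are excluded at entry (exclusion criterion 5), and PHQ-9 and C-SSRS are scheduled at Week 56 and summarized by visit under Section 9.7.1.8.6 whatever the AE classification.

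**Conclusion.** The point holds in its narrow form. Read as written, Section 9.7.1.8.2 keeps out of the treatment-emergent tables an AE that was present before treatment, continuous, no worse on drug and first worse on days 1 to 28 after the last dose, while a new or recurring AE on the same day goes in. This rests on the plain reading that limb 3 has no post-dose window, and on the worsening being recorded as a change in the existing AE rather than as a new one.

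The effect on the tables is probably small and cannot be quantified from the documents. It is tempting to size it by the window's share of observed time: 28/(364 + 28) = 7.1% for a 52-week completer, or 28/(56 + 28) = 33% for a subject who stops at Week 8. Those are shares of calendar time. They say nothing about how many events are affected, and the affected group is a small subset of all AEs. This is a minor wording correction with no bearing on efficacy.

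**What to change.** In the third limb of Section 9.7.1.8.2, add after the words *during treatment* the same parenthesis that limbs 1 and 2 carry, extending the period to 28 days after the last dose. Equivalently, define the treatment-emergent period once and have all three limbs refer to it. Carry the same wording into the SAP.

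The cost is a few words. No new data are needed, because ongoing AEs are already followed through that window, and neither the efficacy analyses nor the clinical conduct of the study changes.
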